10.4. Randomization

This is an open-label study that does not require randomization.

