15.2.3. Secondary Analysis

Safety analysis: To assess clinical safety, adverse events, vital sign measurements, and clinical laboratory information will be summarized. Adverse Events will be coded using the Medical Dictionary for Regulatory Activities (MedDRA). Changes from baseline for clinical laboratory values and vital signs will be summarized over time. Descriptive statistics and shift tables will be generated as appropriate.

The **secondary efficacy/pharmacodynamic analysis** will be performed using the ITT and EE populations and will include:

- Erythroid response, as defined above for primary endpoint, performed using the ITT population.
- For non-transfusion dependent patients, the proportion of patients with an increase of ≥ 1.0 g/dL from pretreatment hemoglobin maintained ≥ 8 weeks.
- For non-transfusion dependent patients, the proportion of patients with an increase of ≥ 1.5 g/dL from pretreatment hemoglobin maintained ≥ 8 weeks.
- For transfusion dependent patients, the proportion of patients who have $\geq 50\%$ reduction in RBC transfusion burden compared to pretreatment using 12-week intervals.
- For transfusion dependent patients, the proportion of patients who have $\geq 50\%$ reduction in RBC transfusion burden compared to pretreatment using 8-week intervals.
- For transfusion dependent patients, the proportion of patients who have no RBC transfusions ≥ 8 weeks.
- Time to erythroid response and duration of erythroid response.
- Change from pretreatment in transfusion burden in transfusion dependent patients
- Change in hemoglobin level in non-transfusion dependent patients
- Change in pre-transfusion hemoglobin levels in transfusion dependent patients
- Change from baseline in erythropoiesis parameters including serum erythropoietin levels, hemoglobin analysis (electrophoresis, globin chain RNA), reticulocytes, and nucleated RBCs
- Change from baseline in hemolysis parameters include haptoglobin, indirect bilirubin, and lactate dehydrogenase (LDH)
- Change from baseline in iron metabolism parameters include serum iron, total iron binding capacity (TIBC), transferrin, calculated transferrin saturation, soluble

transferrin receptor, ferritin, non-transferrin bound iron (NTBI), hepcidin, and liver iron content (LIC) by MRI

- Change from baseline in bone metabolism parameters include bone specific alkaline phosphatase (BSAP) and C-telopeptide of type I collagen (CTX)

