5. STATISTICAL METHODOLOGY

5.1. Definitions

Transfusion Dependent (TD)

Based on protocol, TD patients are defined as those who required ≥ 4 units of RBCs every 8 weeks (confirmed over 6 months prior to Cycle 1 Day 1).

For programming implementation, a patient is defined as TD if the total RBCs is ≥ 11 units during 26 weeks on or prior to Cycle 1 Day 1.

Non-Transfusion dependent (NTD)

NTD patients are those who do not meet the above definition for TD. For programming implementation, NTD patients are defined as those who received < 11 units of RBCs during 26 weeks on or prior to Cycle 1 Day 1.

Baseline Hemoglobin

Baseline hemoglobin will be an average of hemoglobin measurements within 28 days of Cycle 1 Day 1, excluding measurements within 14 days following RBC transfusion.

Baseline Transfusion Burden

Baseline transfusion burden will be calculated as the total amount of RBC transfusions during the 12 weeks on or prior to Cycle 1 day 1.

Baseline for Other Parameters

Baseline erythropoietin (EPO) is defined as the maximum test value within 28 days of Cycle 1 Day 1. For all other parameters, baseline is defined as the last observation on or prior to Cycle 1 Day 1.

Transfusion Unit Conversion

The transfusion amount measured in unit “mL” will be converted to “units” according to medical review.

End of Treatment (EOT)

Procedures and evaluations for the end of treatment visit should be performed 28 days (± 7 days) after the last dose of ACE-536.

End of Study (EOS)

Procedures and evaluations for the end of study visit should be performed 28 days (± 7 days) after the Day 113/EOT visit (56 days after the last dose of ACE-536).

Combined Dose Groups

Low dose group includes patients on 0.2mg/kg and 0.4 mg/kg dose cohorts. High dose group include patients with dose level 0.6 mg/kg and above. Suitable summaries may be presented by low/high dose as specified.

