5.7.2.4. Erythropoiesis Parameters

Blood samples relating to erythropoiesis parameters include serum erythropoietin (EPO) levels, hemoglobin electrophoresis, globin chain RNA, reticulocytes and nucleated RBCs. EPO will be taken at Screening, Day 1 of Cycles 1, 2, 4, EOT, and EOS. Hemoglobin electrophoresis and globin chain RNA will be taken at C1D1, C4D1 and EOT. Reticulocytes

and nucleated RBCs will be taken at Screening, Day 1, 8, and 15 of Cycles 1, 2, 3, 4, 5, EOT and EOS visits. Descriptive statistics of observed values, absolute and percentage change from baseline values at each postbaseline visit will be presented by dose cohort and for TD and NTD separately. Plots of erythropoiesis parameters for both mean observed values and mean percentage change from baseline over time will be presented by dose cohort.

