5.7.4. Subgroup Analysis

Subgroup analyses of erythroid response will be performed with the following baseline factors, for NTD and TD patients separately:

- Age (< 32 and \geq 32)
- Gender (male and female)
- Iron chelation therapy (yes and no)
- Baseline LIC (< 3, 3-5, \geq 5)
- Baseline EPO (< 200 and \geq 200), (< 200, 200-500, and \geq 500), (< 500, and \geq 500)
- Splenectomy (yes and no)

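### Baseline EPO is the higher of two pre-dose values, so comparing single later values with it builds in a fall even if the drug has no effect

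*SAP*

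**What the plan says.** SAP 5.1 gives EPO its own baseline rule: "Baseline erythropoietin (EPO) is defined as the maximum test value within 28 days of Cycle 1 Day 1". The general rule that follows is "For all other parameters, baseline is defined as the last observation on or prior to Cycle 1 Day 1". Hemoglobin and transfusion burden have separate definitions in the same section, an average and a 12-week total. None of these is a maximum.

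The sampling schedule in SAP 5.7.2.4 is "EPO will be taken at Screening, Day 1 of Cycles 1, 2, 4, EOT, and EOS". That gives two values before dosing and single values at each of four later visits. On reporting, the same section says "Descriptive statistics of observed values, absolute and percentage change from baseline values at each postbaseline visit will be presented by dose cohort", and it also plots mean observed values and mean percentage change over time. SAP 5.2 adds the median to the standard summaries.

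Protocol 15.2.3 lists "Change from baseline in erythropoiesis parameters including serum erythropoietin levels" among the secondary efficacy/pharmacodynamic analyses and gives no maximum rule. The SAP gives no reason for the rule and does not list it in 5.13. Baseline EPO is also used in SAP 5.7.4 to form subgroups, with cut points at 200 and 500. Protocol 10.4 says "This is an open-label study that does not require randomization".

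**The concern.** The maximum of two noisy measurements lies above the patient's own average. A single later measurement does not. Subtracting one from the other gives a negative expected change that comes from the selection of the baseline and not from treatment.

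In a randomised trial, the control arm would show the same artefact and the comparison would largely cancel it. This study has no control arm, so within-cohort change is all a reader has. A built-in fall in EPO could be taken for a pharmacodynamic effect, and a true rise could be hidden.

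**Working it through.** The documents give no figure for EPO, so there is nothing of the plan's own to reproduce.

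**Inputs from the documents.** Baseline is the maximum (SAP 5.1). There are two scheduled pre-dose values and single post-dose values (SAP 5.7.2.4). Reporting is as absolute and percentage change, with mean and median (SAP 5.7.2.4 and 5.2).

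**Assumptions not in the documents.** There is no drug effect. EPO is log-normal within a patient. The two pre-dose values and the post-dose value are independent given the patient's level. Within-patient CV is 20, 30 or 40%, with a wider range below.

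**Step 1: proportion falling.** Take three exchangeable continuous values, two before and one after. Each is equally likely to be the largest. The later value exceeds the maximum of the other two with probability 1/3, so 2/3 = 67% of patients show a fall. This needs no CV and no distribution, only exchangeability. With one baseline value it is 1/2.

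**Step 2: size.** Let s = sqrt(ln(1 + CV²)) and let Φ be the standard normal distribution function.
- Mean absolute change, as a share of the true mean: 1 - 2Φ(s/√2).
- Arithmetic mean percentage change: 2·exp(s²)·Φ(-s/√2) - 1.
- Median percentage change: by simulation, 2,000,000 patients per CV.

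Worked at CV 30%: s = sqrt(ln 1.09) = 0.294 and s/√2 = 0.208, so Φ(0.208) = 0.582. Mean absolute change = 1 - 2 × 0.5822 = -16.4%. Mean percentage change = 2 × 1.09 × 0.4178 - 1 = -8.9%.

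**Step 3: the same quantities under the two replacement rules.** With a single last value, arithmetic mean percentage change is exp(s²) - 1 = CV². Results for the mean of two values are from the simulation.

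| Rule and statistic, no drug effect | CV 20% | CV 30% | CV 40% |
|---|---|---|---|
| Maximum of 2: mean absolute change | -11.1% | -16.4% | -21.5% |
| Maximum of 2: median percentage change | -10.5% | -15.0% | -19.3% |
| Maximum of 2: mean percentage change | -7.6% | -8.9% | -8.9% |
| Last value: mean absolute change | 0 | 0 | 0 |
| Last value: median percentage change | 0 | 0 | 0 |
| Last value: mean percentage change | +4.0% | +9.0% | +16.0% |
| Mean of 2: mean absolute change | 0 | 0 | 0 |
| Mean of 2: median percentage change | -1.0% | -2.0% | -3.5% |
| Mean of 2: mean percentage change | +2.0% | +4.5% | +7.9% |

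**Step 4: sensitivity.** From CV 10% to 50%, the maximum rule gives mean absolute change of -5.6% to -26.1% and median percentage change of -5.4% to -23.1%. At an extreme CV of 80%, these are -38.1% and -32.4%, but the arithmetic mean percentage change is +1.5%, because averaging ratios pushes upward.

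Correlation between the two pre-dose values shrinks the bias. For normal values, the expected excess of the maximum is SD × sqrt((1 - ρ)/π). That is 0.564 SD at ρ = 0 and 0.564 × √0.5 = 0.40 SD at ρ = 0.5. If the two pre-dose values are more alike than either is to a later value, the 67% also moves toward 50%.

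**The case against.** The case for leaving the rule alone has real content.

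- **EPO is descriptive.** No hypothesis test is planned (SAP 5.2 and 5.7), and the primary endpoint, sample size and safety analyses do not use this baseline for change. This stands and limits the weight of the point.
- **The data can be re-read.** Observed EPO is summarised and plotted, and all data are listed, so another baseline can be computed. This partly stands. The planned change tables and plot would still carry the artefact, and the SAP does not say whether the pre-dose point in the observed plot is the visit value or the derived maximum.
- **Dose comparisons are less affected.** Cohorts on the same schedule with similar variability share about the same bias. This stands. Within-cohort change remains biased.
- **The plotted statistic moves least.** Mean percentage change falls by only 8 to 9%, and a last-value baseline biases it upward by as much at CV 30% and by more at CV 40%. This stands, so changing the baseline alone is not enough.
- **The size is assumed.** This stands. The direction of the absolute and median changes does not depend on the CV chosen. The 67% needs exchangeability.

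Two stronger readings are tempting. First, a reader might infer that the EPO window admits the Day 22 sample, and the hemoglobin window ("Baseline hemoglobin will be an average of hemoglobin measurements within 28 days of Cycle 1 Day 1") post-dose hemoglobins, since neither is expressly limited to values on or before C1D1. The documents point the other way. Protocol 9.3.2 uses the same idiom looking backward for antibiotics and hydroxyurea. The 28 days match the screening window. Protocol 15.2.2 and footnote 5 of the SAP schedule place the hemoglobin baseline before dosing. SAP 5.7.2.4 reports change at postbaseline visits, of which C2D1 is the first for EPO. Only a wording clarification is warranted.

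Second, a reader might infer that EPO alone departs from a last-value rule. It does not: hemoglobin and transfusion burden differ too. EPO is alone in using a maximum.

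**Conclusion.** The point holds for the maximum of two pre-dose values. As written, the rule biases change from baseline downward in an uncontrolled study. At CVs of 20 to 40%, the bias is about 11 to 21% of the true mean in absolute change, 10 to 19% in median percentage change and 8 to 9% in mean percentage change, with 67% of patients falling instead of 50%. These sizes rest on an assumed CV and on independent log-normal values; correlation between the pre-dose values would make them smaller.

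A reader might conclude that EPO must appear to fall in every patient and every summary. That goes too far. The fall is an expectation over patients, it is absent for anyone with only one value in the window, and the arithmetic mean percentage change can lose it at very high CV. Nor does the rule put the primary endpoint in doubt.

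**What to change.** 1. In SAP 5.1, for change from baseline, define baseline EPO as the last value (the SAP's general rule) or the mean of the values taken on or before C1D1, pre-dose. Both give zero expected absolute change. The mean of two is less noisy: with independent values of variance σ², the change has variance σ² + σ²/2 = 1.5σ², against 2σ² with the last value.
2. In SAP 5.7.2.4, present and plot the median percentage change or the geometric mean ratio to baseline for EPO, in place of the arithmetic mean percentage change. Pair it with the last value or the geometric mean of the pre-dose values, so that the null value is no change.
3. Keep the maximum, if it is wanted, only for the EPO subgroups in 5.7.4, with the reason stated.
4. As a wording clarification, limit the EPO and hemoglobin baseline windows explicitly to values on or before C1D1, pre-dose.

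The cost is a sentence or two in the SAP, one derivation and one change to the EPO tables and plot. No new data are needed.

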5.2. General Considerations

Unless otherwise noted, continuous data will be summarized with the following descriptive statistics: number of observations (n), mean, standard deviation (STD), minimum, median, and maximum. Categorical data will be summarized with frequencies (n) and percentages (%). In cases where missing data cause percentages not to sum to 100, a missing data row will be

provided. Percentages will use column totals as the denominator unless otherwise indicated. For time to event variables, the Kaplan-Meir curves will be presented if the number of patients is more than 5.

All study data will be included in study data listings. Missing data will generally be treated as missing, not imputed, unless otherwise stated.

All summaries will be presented by dose cohort, and may also be presented by low/high dose groups as specified. The summaries may also be presented for TD and NTD patients separately as specified. All summaries will be descriptive. No formal hypothesis testing is planned.

5.3. Disposition of Patients

The number and percentage of patients receiving study treatment who completed the treatment period and study period along with the associated reasons for discontinuation from treatment and/or withdrawal from study will be presented by dose cohort.

5.4. Demographic, Baseline Characteristics, and Disease History

The following baseline and demographic characteristics will be summarised by descriptive statistics by dose cohort for ITT population as well as for TD and NTD patients separately:

- Race, ethnicity, age, gender, height, weight
- Splenectomy (yes or no), iron chelation therapy (yes or no), prior β-thalassemia treatment (yes or no)
- Baseline haemoglobin for NTD patients only and baseline transfusion burden for TD patients only.
- Baseline LIC and serum Ferritin

Demographic and baseline data, medical history, and disease history data will be listed for each patient.

5.5. Study Drug Exposure

Study drug exposure will be descriptively summarized by dose cohort for safety population and will present the duration of exposure, the number of treatment cycles, the total dose administered, the number of patients with dose delay and reduction, and the number of patients with dose increase (for expansion cohort only).

The duration of exposure will be calculated as (last dose date – first dose date) + 21.

The total number of cycles will be summarized by presenting the number and percentage of patients in each category.

The total dose administered is the total amount of doses a patient received during the treatment period.

The number of patients experiencing dose delay and reduction will be summarized by dose cohort. For the expansion cohort, the number of patients with dose increase will also be summarized.

Study drug administration details will be listed for each patient.

5.6. Prior and Concomitant Medication and Procedures

5.6.1. Prior and Concomitant Medication

The prior and concomitant medications are coded with WHO- DDB2E. The medications will be summarized by dose group for the ITT population.

Medications will be assigned as prior or concomitant based on the following rules:

- If both the start and stop date exist and are before the first dose date of study drug, the medication will be counted as prior.
- If the start date is on or after the first dose date of study drug, the medication will be counted as concomitant.
- If the start date is before the first dose date of study drug and the stop date is after the first dose date of study drug or the medication is ongoing, the medication will be counted as prior and concomitant.
- If the start date is missing and the stop date is before the first dose of study drug, the medication will be counted as prior.
- If the start date is missing and the stop date is after the first dose of study drug or the medication is ongoing, the medication will be counted as concomitant.
- If the start and stop dates are missing, the medication will be counted as concomitant.

All prior and concomitant medications will be listed for each patient.

5.6.2. RBC Transfusions

The complete RBC transfusion records prior to and during treatment will be listed for each patient. The hemoglobin values prior to transfusion will also be listed.

5.6.3. Non-Medication Procedures

Non-medication procedures will be coded using MedDRA Version 15.1 or higher. All non-medication procedures will be listed for each patient.

5.7. Efficacy Analyses

All efficacy endpoint will be performed using the ITT population.

All efficacy summaries will be presented by dose cohort and for NTD and TD patients separately. In addition, the dose cohorts will be combined and presented as low dose group and high dose group. Low dose group includes patients on 0.2 and 0.4 mg/kg dose cohorts. High dose group includes patients on 0.6 mg/kg and above. No formal hypothesis testing is planned.

In general, below rules apply to the derivations of efficacy endpoints which utilize hemoglobin and RBC transfusion data unless specified otherwise:

- Hemoglobin measurements within 14 days following RBC transfusion will be excluded from efficacy analysis
- For each patient, all efficacy endpoints will be derived based on an analysis cut-off day, defined as the last dose + 56 days or the last date from transfusion record data, whichever is earlier.

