2. STUDY OBJECTIVES

Primary Objective:

- To evaluate the proportion of β -thalassemia patients who have an erythroid response, defined as: 1) a hemoglobin increase of ≥ 1.5 g/dL from baseline for ≥ 14 days (in the absence of red blood cell [RBC] transfusions) in non-transfusion dependent patients, or 2) $\geq 20\%$ reduction in RBC transfusion burden compared to pretreatment in transfusion dependent patients

Secondary Objectives:

- To evaluate safety and tolerability of ACE-536
- To evaluate the proportion of transfusion dependent patients who have $\geq 50\%$ reduction of RBC transfusion burden compared to pretreatment
- To evaluate the time to erythroid response and duration of erythroid response
- To evaluate the change in hemoglobin level in non-transfusion dependent patients
- To evaluate the change in pre-transfusion hemoglobin levels in transfusion dependent patients
- To evaluate changes in biomarkers of erythropoiesis, hemolysis, iron metabolism and bone metabolism
- To examine the pharmacokinetic (PK) profile of ACE-536 in patients with β -thalassemia

Exploratory Objectives:

- To evaluate biomarkers related to the TGF- β superfamily
- To evaluate self-reported quality of life using the FACT-An and SF-36 questionnaires (expansion cohort only)
- To evaluate change in spleen size by MRI
- To evaluate change in bone mineral density (BMD) by DXA
- To evaluate change in extramedullary hematopoiesis (EMH) mass size by MRI
- To evaluate change in leg ulcer size
- To evaluate change in the 6-minute walk test (6MWT) distance in NTD patients

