Each TD patient in the expansion cohort had a defined "pre-transfusion hemoglobin threshold" which was calculated based on transfusion history and was used for determining when to transfuse during the study. The baseline pre transfusion hemoglobin threshold was the mean of all documented pre-transfusion hemoglobin values during the 12 weeks prior to C1D1. During treatment, if the pre-transfusion hemoglobin value was increased by \geq 1 g/dL compared to the baseline pre-transfusion hemoglobin threshold for that patient, transfusion should be delayed by a minimum of 7 days and/or the number of units transfused should be reduced by 1 or more RBC units. Patients may be transfused at the investigator's discretion for symptoms related to anemia or other requirements (e.g., infection).

Cohort ^a	ACE-536 Dose Level ^b (mg/kg)	Number of Patients
1	0.2	6
2	0.4	6
3	0.6	6
4	0.8	6
5	1.0	6
6	1.25	5
Expansion	0.8	30 ^c
Total (All Cohorts): 64		

^a Cohort escalation was based on SRT review and recommendation to enroll additional cohorts and/or the expansion cohort.

^b The ACE-536 dose level for cohort 1 was 0.2 mg/kg. The dose level indicated in the table for all subsequent cohorts was the maximum dose level that could be recommended by the SRT for escalation per the modified Fibonacci dose escalation scheme.

^c The expansion cohort consisted of 30 patients, including a minimum of 12 patients who were non-transfusion dependent and a minimum of 12 patients who were transfusion dependent (including a minimum of 6 thalassemia major patients with onset of regular transfusions before age 4 years, and a minimum of 6 patients with onset of regular transfusions after age 4 years).

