5.7.3.3. Other Analysis

The following additional exploratory endpoints will be presented in listings only:

- Change in spleen size by MRI (in subset of patients with no prior-splenectomy)
- Change in bone mineral density (BMD) by DXA
- Change in extramedullary hematopoiesis (EMH) mass size by MRI
- Change in leg ulcer size (area)
- Change in the 6-minute walk test (6MWT) distance in NTD patients
- Hormone parameters (including estradiol, free testosterone, and total testosterone)

For the following continuous variables, the descriptive statistics including mean, median and range will be presented by dose cohort:

- Change from pretreatment in transfusion burden in transfusion dependent patients
- Change in hemoglobin level in non-transfusion dependent patients
- Change in pre-transfusion hemoglobin levels in transfusion dependent patients

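### The SAP does not lift its 14-day post-transfusion exclusion for change in pre-transfusion hemoglobin, so transfusion-dependent patients on short gaps give partial or no data to that summary

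*SAP*

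**What the plan says.** SAP 5.7 introduces its derivation rules with "In general, below rules apply to the derivations of efficacy endpoints which utilize hemoglobin and RBC transfusion data unless specified otherwise". The first rule is "Hemoglobin measurements within 14 days following RBC transfusion will be excluded from efficacy analysis".

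The affected endpoint is a secondary objective in SAP Section 2: "To evaluate the change in pre-transfusion hemoglobin levels in transfusion dependent patients". Protocol 8.2 and 15.2.3 give it the same rank. Its only analysis text in the SAP is one line under the exploratory heading, in 5.7.3.3: "Change in pre-transfusion hemoglobin levels in transfusion dependent patients". It is to be described by mean, median and range for each dose cohort. That line gives no derivation, no baseline and no exemption from the 5.7 rule.

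Three other places bear on the point:

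- Protocol 10.2.2 asks for a hemoglobin value just before every on-study transfusion, so the data exist.
- SAP 3.1 (and protocol 9.1) sets, for TD patients in the expansion cohort, a threshold used to decide when to transfuse. It "was the mean of all documented pre-transfusion hemoglobin values during the 12 weeks prior to C1D1", with no 14-day filter.
- SAP 5.6.2 lists the hemoglobin values taken before transfusion.

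**The concern.** Dropping hemoglobin soon after a transfusion makes sense where donor blood could pass for a drug effect, as in the non-transfusion-dependent (NTD) response. A pre-transfusion value is different. It is the level reached before the next transfusion, and the previous transfusion is part of what it measures. When the gap is 14 days or less, the filter removes exactly the values the endpoint is meant to describe.

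The loss is not random with respect to treatment. Whether a value counts depends on the time since the last transfusion, and SAP 3.1 lets a rise in hemoglobin change that time. The dose-escalation cohorts hold 5 or 6 patients each, TD and NTD together (SAP 3.1), so losing one TD patient can alter a cohort summary visibly.

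**Working it through.** **Plan's own figure.** The documents give no figure for this endpoint. Their one design calculation, about 87% power with n = 30, 30% versus 10% and one-sided 0.05, concerns the erythroid response rate. A normal approximation with continuity correction reproduces it: z = [(0.30 − 0.10 − 1/60)·√30 − 1.645·√(0.10·0.90)] / √(0.30·0.70) ≈ 1.11, or 86.7%. It does not enter what follows.

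**Does the rule reach the endpoint?** The 5.7 rule applies unless something else is specified, and 5.7.3.3 specifies nothing. The rest of the plan suggests this reach was not intended:

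- Protocol 15.2.2 states its two-week exclusion in the paragraph on baseline hemoglobin, and 10.8.2 states it for NTD dose titration.
- SAP 5.7.1 repeats the exclusion only in the NTD definition.
- SAP 5.13 does not list its use for this endpoint among the changes from the protocol.

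**Who is affected?** SAP 5.1 says "TD patients are defined as those who required ≥ 4 units of RBCs every 8 weeks", with no upper limit. For programming, "a patient is defined as TD if the total RBCs is ≥ 11 units during 26 weeks". Assume even spacing with u units per transfusion; u is not in the documents.

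| u | Gap at 4 units per 8 weeks = 56u/4 | Gap at 11 units per 26 weeks = 182u/11 | Units per 8 weeks giving a 14-day gap = 56u/14 |
|---|---|---|---|
| 1 | 14 days | 16.5 days | 4 |
| 2 | 28 days | 33.1 days | 8 |
| 3 | 42 days | 49.6 days | 12 |

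The rule therefore affects patients on small, frequent transfusions, or those well above the entry burden. The TD definition admits both.

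**How much is dropped?** On a fixed 14-day schedule, every value is dropped. With variable gaps, the simulated share over 84 days is below. Assumptions: gaps normal, rounded to whole days, at least 5 days, SD 2 or 4 days; a value is dropped if the gap is 14 days or less.

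| Mean gap | SD 2 | SD 4 |
|---|---|---|
| 14 days | 61.1% | 56.9% |
| 17.5 days | 7.3% | 24.3% |
| 21 days | 0.1% | 5.9% |
| 28 days | 0.0% | 0.0% |

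If day 14 itself were kept, the 14-day row would read 41.2% and 47.0%, and a fixed 14-day schedule would lose nothing. The SAP does not say how the boundary day is counted.

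**How does treatment change inclusion?** When pre-transfusion hemoglobin is at least 1 g/dL above the threshold, SAP 3.1 calls for a delay of at least 7 days, fewer units, or both. For a patient on a 14-day gap:

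- Delay: 14 + 7 = 21 days, so the value before the delayed transfusion is kept.
- Fewer units at an unchanged gap: 14 days, so the raised value is dropped.

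The same rise can bring a value in or leave it out.

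**Which baseline?** None is assigned. SAP 5.1 offers a filtered 28-day average for hemoglobin and the last observation for other parameters; SAP 3.1 offers the unfiltered 12-week mean, but as a transfusion threshold. Under the filtered average, a patient always on gaps of 14 days or less may have no baseline and therefore no change score.

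**The case against.** The strongest reply is that this is a small matter of clarification. The rule is worded as a general one, the values stay in the listings, and the endpoint is descriptive with no hypothesis test. The TD primary and responder endpoints count transfused units, which a hemoglobin filter does not touch. All of that stands and limits the consequence. It does not supply the missing exemption: a programmer following the SAP would apply the filter.

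A reader might go further and infer four things that the documents do not support.

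- *The kept values are selected toward success.* This needs a filtered on-treatment series set against an unfiltered baseline, a pairing the SAP does not state. It also needs delay to be the usual action, whereas fewer units at the same gap would exclude raised values. The threshold rule covers expansion-cohort TD patients only, and gaps can change at the investigator's discretion. An illustrative simulation does show inflation, from 0.40 to 0.43 g/dL if 10% of TD patients have 14-day gaps and from 0.40 to 0.48 at 25%. It does so only by assuming an unfiltered baseline, delay at every rise of 1 g/dL or more, 24-day gaps in the other patients, a true mean change of 0.5 g/dL, and SDs of 0.7 between and 0.5 within patients.
- *A patient at the entry threshold loses every value.* This assumes one unit per transfusion. At two units the gap is 28 days. At the programmed cut-off it is 16.5 days even with single units.
- *SAP 3.1 contradicts 5.7.* Section 3.1 defines a threshold for transfusion decisions, not a declared analysis baseline.
- *The data are deleted.* They leave the summary, not the record.

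**Conclusion.** The point holds as a rule applied to a measure it does not suit. As the SAP stands, pre-transfusion hemoglobin drawn 14 days or less after the previous transfusion is left out of the summary of a secondary objective, and inclusion depends on an interval that treatment can alter.

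The loss ranges from nearly nothing, if TD patients are transfused every three to four weeks, to every value for a patient on a fixed 14-day schedule. The documents do not say where the trial's patients lie in that range, and they do not fix the direction of any bias. The gap arithmetic rests on even spacing and assumed units per transfusion; the simulated shares rest on assumed gap distributions. The correction is worth making because it is cheap and the endpoint is a stated objective, not because a distortion of known size has been shown.

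**What to change.** Make these changes in SAP 5.7 and 5.7.3.3, and record them in 5.13:

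1. State that, for change in pre-transfusion hemoglobin, the 14-day exclusion does not apply to hemoglobin drawn just before a transfusion in TD patients.
2. Define the analysis baseline, for TD patients in every cohort, as the average of every pre-transfusion hemoglobin on record in the 12 weeks ahead of C1D1.
3. Use every on-treatment pre-transfusion value up to the analysis cut-off day already set in 5.7.
4. Report the number of patients and values contributing, by cohort. Give the version with the 14-day filter as a sensitivity summary, stating whether day 14 is in or out.

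Keep the exclusion for the NTD hemoglobin endpoints.

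The cost is a few sentences of SAP text and one extra descriptive table. Hemoglobin before on-study transfusions and 12 weeks of historical hemoglobin are already collected under the protocol, and patient care does not change.
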